Preliminary Analysis. For all variables, we will examine the distribution for potential nonnormality and outliers. If necessary, appropriate data transformations or alternative data analysis procedures (e.g., nonparametric, bootstrapping) will be used prior to data unblinding. Prior to outcome analyses, baseline demographic and outcome variables will be assessed for baseline equivalency. Categorical variables will be analyzed using chi-square tests; continuous variable differences will be assessed using pooled t-tests. Per missing data design (see **Missing Data**), if baseline differences are detected, these covariates will then be included in the final model as auxiliary variables to improve the plausibility of assuming data is MAR.⁹⁶

Primary Analyses in Support of the Specific Aims. **Aim 1 Hypothesis:** Participants receiving CBT-TS will be significantly more likely to initiate psychosocial pain treatment than participants in the control condition. Treatment initiation of psychosocial pain treatment will be treated as a binary outcome variable (0|1). A Cox Proportional Survival Analysis.⁹⁷ will be conducted to examine treatment initiation by the 6-month follow-up. This approach is like logistic regression except it accounts for missing data across the follow-up timepoints. Condition will be entered into the model as a predictor of whether a participant reported attending treatment by the 6-month follow-up. The assumption of proportionality will be tested in this model. A secondary logistic regression analysis will be conducted to examine treatment initiation by the end of the 6-month follow-up using worst case imputation of missing outcome to test robustness of any effects. Additional secondary analyses to demonstrate treatment robustness will be treatment initiation by the 1-month and 3-month follow-ups.

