Aim 2 Hypothesis: Treatment initiation for African American participants receiving CBT will be moderated by CBT treatment components, including individualization, non-judgment, self-expert, collaboration, and empowerment. We will restrict these analyses to African American participants and will include treatment condition, CBT treatment components, and condition by components interaction terms.

Exploratory: Explore the effect of race-related stress on treatment initiation and retention to other non-pharmacological pain treatments among African American Veterans receiving opioid analgesics for chronic pain. African Americans participants who experience higher levels/more

race-related stress will be significantly less likely to initiate or complete other non-pharmacological pain treatments for chronic pain.

Missing Data. An intent-to-treat (ITT) approach will be used, including all participants randomized to a treatment condition. Missing data in the full analysis set will occur if participants discontinue prior to the end of the study or do not complete an outcome measure. Participants will not be discontinued from the study because of non-adherence and all will remain in the study unless consent is withdrawn or if there are concerns regarding participant safety. Missing data for the ITT analysis set will be addressed using robust full information maximum likelihood (FIML), which is superior to most alternative missing data approaches even when data is missing completely at random (MCAR) or missing at random (MAR).^{96,98} Although the use of FIML will result in the least biased parameters, regardless of data missingness, several approaches will be undertaken to better understand the exact mechanisms for missing data. Little's MCAR test will be applied to all final models to determine whether data can be considered MCAR. Further, the results of analyses using study completers will be compared with results using the ITT approach to test sensitivity of study conclusions to study discontinuations. Baseline differences also will be explored between treatment completers and those that discontinue across study and demographic variables. If baseline differences are detected, these covariates will then be included in the final model as auxiliary variables to improve the plausibility of assuming data is MAR.⁹⁶

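### The plan says FIML is least biased whatever the missingness, and no analysis of Aim 3's four participant-reported outcomes relaxes missing at random

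*Combined protocol and SAP*

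**What the plan says.** The Missing Data paragraph of Section 5.7 applies robust FIML to the intent-to-treat set and calls it "superior to most alternative missing data approaches even when data is missing completely at random (MCAR) or missing at random (MAR"). Missing not at random (MNAR) is not named anywhere in the document. The paragraph then asserts: "Although the use of FIML will result in the least biased parameters, regardless of data missingness".

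Three supporting steps follow:

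- Little's "MCAR test will be applied to all final models to determine whether data can be considered MCAR".
- A completer analysis: "the results of analyses using study completers will be compared with results using the ITT approach to test sensitivity of study conclusions".
- A baseline comparison of those who complete and those who discontinue. Where they differ, "these covariates will then be included in the final model as auxiliary variables to improve the plausibility of assuming data is MAR". The Preliminary Analysis paragraph adds auxiliary covariates in the same way when the arms differ at baseline.

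For Aim 1, Section 5.7 adds a logistic regression "using worst case imputation of missing outcome to test robustness of any effects". For Aim 3, the only robustness analysis moves the visit on which time is centred.

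**The concern.** FIML gives consistent estimates when missingness depends only on observed data. If people leave because of a worsening that was never recorded, and this differs by arm, the estimated treatment effect is biased. A blanket assurance covering every kind of missingness tells the reader that this risk has been dealt with.

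The steps offered as support do not address it. Little's test concerns missing completely at random and cannot separate MAR from MNAR. A completer analysis makes a stronger assumption than FIML, so agreement between the two does not show that MAR holds. Auxiliary covariates make MAR more believable but do not examine what happens if it fails.

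The exposure is uneven. Under Section 5.5, pain severity, pain interference and physical functioning come from the PROMIS-29 and misuse risk from the COMM, so a missed assessment is a missing value. Opioid dose, treatment initiation and session counts come from the medical record and depend much less on attendance. The one analysis that leaves MAR is thus attached to a record-based outcome, while the outcomes most open to dropout have none.

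**Working it through.** **The plan's own figure.** Power Analysis and Sample Size raises N from 250 to 300 by a 20% increase: 250 × 1.20 = 300, which reproduces. The loss this covers is 1 − 250/300 = 16.7%. The 250 came from simulation with no numeric effect size given, so it cannot be re-derived.

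**Detectable difference.** Assuming a two-sided 0.05 test (sidedness is not stated) and 80% power, with 125 per arm: (1.960 + 0.842) × √(2/125) = 0.354 SD.

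**Bias under MNAR.** If a share m of one arm is missing and those people are δ SD worse than MAR predicts, that arm's mean is wrong by m × δ. With the same δ in both arms, the contrast is wrong by (m₁ − m₀) × δ. The documents give neither δ nor the pattern by arm. Here δ = 0.5 in the CBT-TS arm only, and 20% and 25% missing, are assumptions. SE = 2/√(number analysed), with no credit for baseline adjustment. The last column is P(Z > 1.96 − bias/SE) when there is no true effect.

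| Missing | Analysed | SE | Bias at δ = 0.5 | Nominal rate favouring CBT-TS (2.5% expected) |
|---|---|---|---|---|
| 16.7% | 250 | 0.126 | 0.083 | 9.7% |
| 20% | 240 | 0.129 | 0.100 | 11.8% |
| 25% | 225 | 0.133 | 0.125 | 15.3% |

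Smaller shifts give less: at 20% missing, δ = 0.2 and 0.3 give 0.04 and 0.06 SD. With δ = 0.5 in both arms, the bias is 0 if missing shares are equal, 0.05 SD at 15% against 25%, and 0.10 SD at 10% against 30%.

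**Does the completer comparison reveal it?** A simulation used 400 replicates, 150 per arm, a baseline and three follow-ups, about 20% missing at month 6 and no true effect. Negative values favour CBT-TS; the three figures are for within-person correlations 0.4, 0.6 and 0.8.

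| Dropout | Maximum likelihood (SD) | Completers (SD) |
|---|---|---|
| Depends on unseen month-6 value, CBT-TS arm only | −0.11, −0.08, −0.05 | −0.14, −0.15, −0.15 |
| As above, opposite directions in the two arms | −0.22, −0.16, −0.08 | about −0.29 throughout |
| MAR, or the same MNAR mechanism in both arms | within about 0.02 of 0 | within about 0.02 of 0 |

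In the arm-dependent cases both estimates err in the same direction, so their difference does not bound the bias. At correlation 0.4 in the one-arm case they differ by only about 0.03 SD, while maximum likelihood is off by 0.11 SD.

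**What a tipping point would show.** Suppose an effect of 0.36 SD is observed with 20% missing. Significance is lost when 0.36 − 0.20 × δ = 1.96 × 0.129, that is at δ of about 0.53 SD in the CBT-TS arm. At 10%, 16.7% and 30% missing the value is about 1.21, 0.67 and 0.30 SD.

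**The case against.** The strongest reply is that the plan is better protected than the quoted sentence suggests. It adds auxiliary covariates in two places and speaks openly of assuming MAR, so a reader who infers that it rests on Little's test and a completer analysis alone, or never recognises MAR as an assumption, goes too far. That stands, but these steps support MAR and do not test departures from it.

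Secondly, least biased is a comparative claim, not a claim of no bias, and in the one-arm and opposite-direction simulations FIML did beat completers. That also stands, and nothing here argues against FIML as the main analysis. The claim still fails as worded, because under MNAR a correctly specified pattern-mixture model would be less biased.

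Thirdly, informative dropout that differs by arm may not occur. Both arms receive one session of about 45 minutes, and non-adherence is not a ground for discontinuation, so similar dropout in both arms is plausible and the bias would then be near zero. Against that, Section 5.8 lets the investigator remove participants for reasons such as extreme distress, which the last assessment may not have captured. The documents do not settle which pattern will arise.

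Fourthly, the 12% is a single-test rate, and the plan applies Benjamini-Hochberg. If the five Aim 3 outcomes form the family (not stated) and only one is biased, a smallest-p threshold of 0.01 gives P(Z > 2.576 − 0.10/0.129) = 3.6% against 0.5%. Inflation remains, but 12% must not be read as the trial's false-positive rate.

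**Conclusion.** The point holds in a limited form. The statement about FIML is wrong, and no analysis in the document relaxes MAR for the four participant-reported Aim 3 outcomes.

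The size is conditional. With 16.7% to 25% missing and a 0.5 SD shift in the CBT-TS arm only, the bias is 0.08 to 0.13 SD. Matched to the number analysed, that is about 24% (0.083/0.354) to 33% (0.125/0.374) of the detectable difference, enough to change a borderline result. With the same shift and equal loss in both arms it is near zero.

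A reader might infer that the Aim 3 results will be biased, or that the trial's main conclusion is at risk. The documents support neither. The shift and its restriction to one arm are assumptions. Aim 3 is a secondary goal in Section 6.0, and the primary outcome comes from records and has its own worst-case analysis. Confidence is high that the MNAR analysis is absent and low on how much harm would follow.

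**What to change.** In the Missing Data paragraph of Section 5.7:

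1. Strike the qualifier extending the claim to any missingness, and state that the Aim 3 analysis is valid under MAR.
2. Add, before unblinding, a prespecified delta-adjusted (pattern-mixture) analysis of the 6-month contrast for pain severity, pain interference, physical functioning and misuse risk. Shift missing values in the worse direction over a stated range, for example 0 to 1 SD, in both arms and in each arm alone, and report the shift at which the conclusion changes.
3. Name this as the sensitivity test for discontinuation. Little's test and the completer comparison can stay as descriptive analyses, and the auxiliary-covariate step is unaffected.

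The cost is one extra sensitivity analysis on data already held, with modest programming and no new participants or visits. The downside is that a borderline Aim 3 result may have to be reported as less robust.

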CBT is ideally suited to modify beliefs interfering with engagement in psychosocial pain treatment. The mechanism behind CBT's efficacy comes from its demonstrated ability to change beliefs, which serves to change behavior (in the case of the current study, treatment initiation and retention).⁶⁹⁻⁷¹ CBT is effective for a wide range of conditions,^{21,69,72} is efficacious when delivered via telehealth,⁷³ and can be administered by individuals other than highly trained mental health professionals.⁷⁴ [name] (co-I) has developed CBT for Treatment Seeking (CBT-TS), which specifically targets treatment beliefs that interfere with treatment seeking. CBT-TS is backed by strong evidence that it increases treatment initiation and retention through changing beliefs. The current study will address the need of increasing the initiation of and retention to psychosocial pain treatments by modifying beliefs that are interfering with treatment engagement.

Conceptual Model. CBT-TS targets beliefs interfering with engagement, which will include beliefs about opioid analgesics, exaggerated negative thoughts about one's ability to address pain (i.e., helplessness-related catastrophizing, fear-avoidance beliefs, pain-related self-efficacy), and psychosocial and other non-pharmacological pain treatment. CBT-TS may also

increase the belief that they can manage their pain providing hope that their functioning can improve. By addressing such beliefs (e.g., “opioids are the only thing that helps me sleep”), patients will be more willing to engage in psychosocial pain treatments. Treatment engagement will then reduce their reliance on opioids as well as improve physical functioning, reduce pain severity, and pain-related interference in activity. CBT-TS may also change beliefs about a wide range of treatments including other non-pharmacological pain treatments and non-pain treatment (e.g., SUD, mental health), which may also impact downstream clinical outcomes.

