5.5 Study Evaluations

Medical Record Review and Treatment Utilization Form (TUF). Treatment utilization will be assessed through medical record review. The measure can be found in the **Appendix**. CAPRI and Joint Longitudinal Viewer will be used to access medical records. These are used at every VAMC and regional office and are accessible from every VA site of care. We will abstract data related to treatment utilization and medications across VHA facilities, including types of service (e.g., CBT-CP, chiropractic care), dates of service, number of sessions, and type and dose of medications. Non-VA medications known to VA providers and non-VA treatment notes are also included in the medical record. This data will be abstracted as available. Treatment initiation of psychosocial pain treatment is defined as attending at least one session of CBT-CP, ACT, or MBSR. We will also utilize data extraction from the Corporate Data Warehouse (CDW) to initially capture treatment utilization from medical records to assist in the medical record review. CDW contains financial, enrollment, demographic, diagnostic, treatment utilization, and other data across Veterans from 1979 to present. For training of the medical record chart review, the research staff will code 12 charts unrelated to the study and then meet to discuss and resolve differences. During the review for the study, they will overlap on 10 charts to facilitate agreement and ongoing discussion of differences will be addressed as needed. Drs. [name] and [name] will make the final decisions.

We will also collect self-report data on non-VHA care not identified in the medical record. *Self-report data will be exploratory* to evaluate the extent to which treatment was utilized outside the VHA and will not be included in the analyses of the primary and secondary outcomes. Participants will be asked at baseline and each follow-up period whether they have initiated treatments and the number of sessions for each type of treatment they have attended since the previous assessment. We will ask participants to provide information about where the treatment was received, and type of treatment (e.g., CBT-CP, MBSR, chiropractic, acupuncture).

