Overdose Risk Behavior Questionnaire (ORBQ). The ORBQ assesses the frequency of past-month engagement in behaviors that are associated with overdose. Higher scores on the ORBQ are associated with number of prior overdoses.⁹⁰

Opioid Dose. The TUF will be used to record information on opioid dose. Opioid type, days supply, and dose will be assessed through access to the medical record. [name] will assist us in the conversion of dose to MEDD as needed.

Table 5. Assessment of the uptake of other relevant treatment and non-opioid analgesics

Other non-pharmacological pain treatments	Other relevant treatment	Non-opioid analgesics

 • Other psychosocial interventions (e.g., hypnotherapy; relaxation training) • Movement-based interventions (e.g., exercise, aquatic therapy, yoga, tai chi) • Manual therapy (e.g., acupuncture, chiropractic care, massage) 	
 • Substance use disorder, including meds • Mental Health, including meds • Nutrition/Diet • Weight loss (MOVE!) • Vocational rehabilitation 	
 • NSAIDs • Muscle relaxants • Anticonvulsants • Anti-depressants • Other analgesics • Medical cannabis

5.5.14. Other relevant treatment utilization. Using a similar data extraction tool as the TUF, we will assess if participants initiate other relevant types of treatment (e.g., mental health, weight loss, substance use interventions; see Table 5). Additionally, we will track if patients start using prescription and non-prescription non-opioid analgesics.

5.5.15. Substance Use Disorder Screener. Lifetime and past three-month possible opioid disorders will be assessed using the NIDA-modified Alcohol, Smoking, and Substance Involvement Screening Test (ASSIST).⁹¹ Respondents are asked to indicate the frequency with which they experience 8 substance-related problems, including “street” opioids and prescription opioids. Scores ranging from 0-3 suggest lower risk, 4-26 suggest moderate risk, and 27 and higher suggest high risk.

5.5.16. Demographics and military background. At screening, we will assess participants’ military background (e.g., service branch, years in service, deployment history), gender, age, educational background, employment, income, race, ethnicity, and marital status.

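### For the four self-reported Aim 3 outcomes, missing-data auxiliary variables are drawn only from baseline, although chart-recorded engagement and opioid dose should usually be known for participants who stop answering

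*Combined protocol and SAP*

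**What the plan says.** Section 5.7 (Missing Data) uses robust FIML for the intent-to-treat set. It has one rule for finding auxiliary variables related to dropout: "Baseline differences also will be explored between treatment completers and those that discontinue across study and demographic variables". Any variable that differs is then used: "If baseline differences are detected, these covariates will then be included in the final model as auxiliary variables". The Preliminary Analysis paragraph has a second rule, on differences between arms, and it is also limited to baseline: "Prior to outcome analyses, baseline demographic and outcome variables will be assessed for baseline equivalency".

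The Aim 3 model in section 5.7 contains condition, time, their interaction and the baseline value of the outcome. No post-randomisation chart variable is named as an auxiliary.

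Section 5.5 describes data that exist beyond the questionnaires. On sessions and medicines: "We will abstract data related to treatment utilization and medications across VHA facilities". On dose: "Opioid type, days supply, and dose will be assessed through access to the medical record". Under Missing Data, participants stay in the study unless they withdraw consent or there is a safety concern. The conceptual model in section 2.0 makes engagement the route to clinical benefit: "Treatment engagement will then reduce their reliance on opioids as well as improve physical functioning, reduce pain severity".

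**The concern.** FIML is valid when data are missing at random given the variables in the model. The plan acknowledges this by adding auxiliary variables to make that assumption more credible, but it searches only among variables measured before the intervention could act. On the trial's own theory, the variable most closely tied to later pain and function is whether the participant started treatment, and that is recorded in the chart.

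Suppose starters are more, or less, likely to keep answering. The observed scores then over- or under-represent starters. CBT-TS is designed to change the number of starters, so the distortion need not cancel between arms. What is at stake is the arm contrast for pain severity, pain interference, physical functioning and COMM, which are four of the five Aim 3 outcomes.

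The planned checks do not cover this. Little's test addresses missing completely at random, not missing at random given the model. The comparison of completers with the intent-to-treat result can agree while both are off, as shown in the working.

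**Working it through.** **The plan's own figures.** Section 5.7 raises N = 250 by 20%: 250 × 1.20 = 300, which reproduces. Its Monte Carlo inputs are not given. For scale, 125 per arm at two-sided 5% and 80% power detects (1.96 + 0.842) × √(2/125) = 0.354 SD, which fits the plan's description of small-to-moderate effects.

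**Inputs not in the documents (all assumed).** Initiation by arm, dropout by engagement, the effect of engagement on the month-6 score (β), and a within-person correlation of 0.6.

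**Hand calculation.** In an arm with initiation p and month-6 dropout dE (engaged) and dN (not engaged), the engaged share among those observed is

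p′ = p(1−dE) / [p(1−dE) + (1−p)(1−dN)].

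The observed mean shifts by β(p′−p), and the bias in the contrast is the difference of the two shifts. This is the bias of a completer analysis. FIML on baseline and earlier scores removes only part of it.

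*Same link in both arms.* Initiation is 20% vs 40%, dropout 5% if engaged and 27% if not, β = −0.5 SD.
- CBT-TS: p′ = 0.38/(0.38 + 0.438) = 0.4645; shift −0.5 × 0.0645 = −0.0323.
- Control: p′ = 0.19/(0.19 + 0.584) = 0.2455; shift −0.5 × 0.0455 = −0.0227.
- Bias: about −0.0095 SD.

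*Link only under CBT-TS.* Dropout is 5%/30% there and 20%/20% in control.
- CBT-TS: p′ = 0.38/(0.38 + 0.42) = 0.475; shift −0.0375. Control: no shift.
- Bias: −0.0375 SD.

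**Large-sample simulation of FIML** (1.5 million per arm; baseline and months 1, 3 and 6; monotone dropout). Dropout is shown as engaged/not engaged.

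| Initiation, control vs CBT-TS | Dropout | True difference | FIML without chart data | Bias (SD) |
|---|---|---|---|---|
| 20% vs 40% | 5%/27% both arms | −0.1021 | −0.1111 | −0.0090 |
| 10% vs 30% | 5%/25% both arms | −0.1019 | −0.1153 | −0.0135 |
| 20% vs 40% | 0%/40% both arms | −0.1021 | −0.1169 | −0.0148 |
| 20% vs 40% | 35%/14% both arms | −0.1021 | −0.0915 | +0.0106 |
| 40% vs 60% | 10%/30% both arms | −0.1017 | −0.1008 | +0.0009 |
| 20% vs 40% | CBT-TS 5%/30%, control 20%/20% | −0.0992 | −0.1346 | −0.0353 |
| 20% vs 40% | control 5%/24%, CBT-TS 20%/20% | −0.0992 | −0.0812 | +0.0180 |
| 40% vs 40% | CBT-TS 5%/30%, control 20%/20% | 0.0009 | −0.0345 | −0.0353 |
| 20% vs 40%, β = −0.8 | CBT-TS 5%/40%, control 20%/20% | −0.1592 | −0.2433 | −0.0841 |

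With engagement as an auxiliary variable, the estimate came within 0.001 SD of the truth in every row. There was no bias when β = 0, or when initiation and dropout were the same in both arms. In the first row the completer estimate was −0.1113 against −0.1111 for FIML, so the planned completer comparison would have shown agreement.

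**At trial size** (N = 300, initiation 20% vs 35%, β worth 0.5 SD, about 20% lost; 1,500 replicates per scenario). The bias was 0.004 to 0.037 SD, and the SD of the estimate was 0.104 to 0.107 with or without the auxiliary. A further run on these dropout rates used one auxiliary and then seven (initiation, sessions and opioid dose over time). Both removed the bias to within about 0.001 SD with no meaningful loss of precision.

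**Against the standard error.** 0.037/0.105 = 0.35 standard errors. Under a null effect, two-sided type I error becomes Φ(−1.96 + 0.35) + Φ(−1.96 − 0.35), about 6.4% instead of 5%.

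**The case against.** A reader might infer that dropout will bias all the Aim 3 effects, or that they will be overstated by 40% to 60%. The documents support neither.

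- Nothing in them says that dropout depends on engagement. The bias is conditional and can take either sign.
- Opioid dose, the fifth Aim 3 outcome, is read from the chart.
- Such percentages arise at trial size only when the dropout link is assumed to exist under CBT-TS alone or to reverse in control, and they are fractions of an assumed effect of about 0.06 SD. Against a detectable 0.354 SD, a bias of 0.004 to 0.037 SD is about 1% to 10%.

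The repeated-measures model also uses month-1 and month-3 scores, which absorb part of any early engagement effect. The exploratory structural equation model examines initiation, pain and opioid outcomes together at month 6. Finally, complete chart data for non-responders are inferred, not stated. The plan foresees some missing initiation data (worst-case imputation under Aim 1), and non-VHA care absent from the record is known only from self-report.

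These points limit the size and certainty of the concern, and all of them stand. They do not remove it. Both auxiliary rules remain baseline-only, the structural equation model is not the Aim 3 analysis, and incomplete chart data still carry more about dropouts than no chart data.

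**Conclusion.** The concern holds as a conditional one, for pain severity, pain interference, physical functioning and COMM only. The plan leaves out of its missing-data model the post-randomisation variables that its own theory links to these scores and that it already collects.

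Bias needs two things: engagement must predict both dropout and the missing score beyond earlier scores, and initiation or the dropout link must differ by arm. Under the assumed inputs it is about 0.004 to 0.015 SD with the same link in both arms (near zero in one setting). With an arm-specific link it is about 0.02 to 0.04 SD, reaching 0.08 SD only with a 0.8 SD engagement effect and up to 40% dropout. That is small against a standard error of about 0.10 SD, but could matter if the downstream effect is itself small. The case for change rests on the remedy using data already collected, not on a large expected bias. It also assumes that chart abstraction continues for participants who stop answering without withdrawing consent.

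**What to change.** In the Missing Data part of section 5.7, name in advance a small set of chart-recorded auxiliary variables for the four self-reported outcomes: psychosocial treatment initiation or cumulative sessions (transformed if skewed), and morphine equivalent daily dose at 1, 3 and 6 months. Include them regardless of any significance test. Enter them as saturated correlates, or in the imputation model if multiple imputation is used. They must not be covariates in the treatment-effect model, because the intervention can change them and adjusting for them would change the effect being estimated. Sessions of other non-pharmacological treatment may be added if the model converges.

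The cost is plan wording and a slightly larger model, with some redundancy because initiation is defined by attending at least one session. Chart data may be incomplete after withdrawal of consent or for non-VHA care. The plan should state whether abstraction continues for participants who stop responding, and what happens to it once consent is withdrawn.

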Power Analysis and Sample Size. A balanced randomization scheme (1:1) will be used for this trial. Power to detect the primary effects of interest for the Aim 1 Hypothesis involve testing whether CBT-TS, compared to the education control condition, increases treatment initiation of psychosocial pain treatment. Power to detect the primary effects of interest for the Aim 2 Hypothesis involve testing whether CBT-TS, compared to the education control condition, increases treatment retention. Power to detect the primary effects of interest for the Aim 3 Hypothesis involve testing whether CBT-TS, compared to the education control conditions, improves pain and opioid outcomes. Sample size was determined using Monte Carlo simulation studies (with 10,000 replications). For each of the hypotheses, it was determined that with a sample size of $N = 250$ we would have at least 80% power with an $\alpha = 0.05$ to find small effects of condition on treatment initiation and small-to-moderate effects on all other direct effects. This includes adequate power to detect all significant indirect effects. To adjust for potential attrition, the sample size was increased by 20%, resulting in a final sample of $N = 300$. Power analyses for the mediation models ($\alpha = .05$, $1 - \beta = .80$) indicates that with 300 participants we will be adequately powered to find mediation in the presence of small-to-medium paths from condition to the potential mediators and from the potential mediators to the primary (treatment initiation) and two secondary outcomes (pain and opioid clinical outcomes).

Type 1 Error Protection. To help control for Type 1 error, the Benjamini-Hochberg method will be used to adjust for the multiple comparisons proposed in the current study.⁹⁹ This method adjusts for multiple comparisons by controlling false discovery rate instead of family-wise error rate. It is less conservative than the more traditional Bonferroni methods, yet still provides adequate protection against Type 1 error and is the optimal solution to the multiple comparison problem in most practical situations.

Data storage, security, and confidentiality

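### The Benjamini-Hochberg family is undefined and does not exempt the primary hypothesis, so the 80% power stated for Aim 1 at alpha 0.05 is not shown under the planned adjustment

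*Combined protocol and SAP*

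**What the plan says.** Under Power Analysis and Sample Size (section 5.7), the plan reports simulation-based power for each hypothesis: "with a sample size of $N = 250$ we would have at least 80% power", at alpha 0.05, for "small effects of condition on treatment initiation and small-to-moderate effects on all other direct effects". The same paragraph raises 250 to 300 for attrition. It does not mention multiplicity.

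The next paragraph, Type 1 Error Protection, says that "the Benjamini-Hochberg method will be used to adjust for the multiple comparisons proposed in the current study". It explains that "This method adjusts for multiple comparisons by controlling false discovery rate instead of family-wise error rate". It does not list the tests, count them, give the FDR level, or say whether Aim 1 is inside or outside the adjustment.

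The ranking of outcomes is clearer. The power paragraph names treatment initiation as primary and the pain and opioid outcomes as secondary. Section 6.0 describes retention and the pain and opioid outcomes as secondary goals. No testing order or gatekeeping follows from that ranking. Section 5.7 also places Aims 1, 2 and 3 together under one run-in heading as primary analyses. Aim 3 has five outcomes: pain severity, pain interference, physical functioning, opioid dose and risk of misuse.

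**The concern.** A single primary hypothesis powered at 0.05 would normally be tested at 0.05. Under the Benjamini-Hochberg rule as written, the Aim 1 threshold lies anywhere between q/m and q, where m is the number of tests in the family and q is the FDR level. Where it falls depends on the other p-values.

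Two things are at stake. First, the primary conclusion can turn on outcomes that the protocol treats as downstream of engagement. One session could plausibly raise initiation without moving pain, dose or misuse within six months, and that is the case in which the rule penalises Aim 1 most. Second, the power that justifies the sample size was stated for a different rule from the one that will be applied. Because the family is open, it could also be settled after the p-values are known. Keeping the investigators blind to what the arm codes mean does not prevent this, since p-values under coded arms already show which choice gives significance.

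**Working it through.** **Inputs from the plan (section 5.7).** Power of at least 80%; alpha 0.05; N = 250 analysed, 300 randomised 1:1; one Aim 1 test, one Aim 2 test and five Aim 3 outcomes, so 1 + 1 + 5 = 7. The count of seven is mine, as the plan gives none.

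**Assumptions.** Power is exactly 80% at N = 250; tests are two-sided; q = 0.05; test statistics are normal and, at first, independent.

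**The plan's own figures.** 250 × 1.2 = 300 reproduces. The 80% cannot be reproduced, because the effects carry only verbal labels, with no rate, hazard ratio, odds ratio or standardised difference. I therefore take the 80% as given and ask what the adjustment does to it.

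**Signal.** 80% power at two-sided 0.05 implies a mean test statistic of 1.960 + 0.842 = 2.802 at N = 250. At N = 300 it is 2.802 × √(300/250) = 3.069, and unadjusted power is Φ(3.069 − 1.960) = 87%.

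**Floor.** The strictest threshold is 0.05/7 = 0.0071, with critical value 2.690. Power there is Φ(2.802 − 2.690) = 54% at N = 250 and Φ(3.069 − 2.690) = 65% at N = 300. Holding 80% at that floor needs 250 × ((2.690 + 0.842)/2.802)², about 398 analysed in two equal arms.

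**Full Benjamini-Hochberg, simulated, m = 7.** At least 200,000 replications per scenario except the 30% row, which I ran with 400,000:

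| The other six tests | Aim 1 power, N = 250 | Aim 1 power, N = 300 |
|---|---|---|
| all null | 55% | 65% |
| each with 30% power at N = 250 | 63% | 74% |
| three as strong as Aim 1, three null | 69% | 79% |
| all as strong as Aim 1 | 77% | 85% |

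With correlation 0.3 between tests, the N = 250 values for the null, half-real and all-real rows are 55%, 68% and 76%.

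**A worked p-value.** With m = 7 and q = 0.05, the first four steps are 0.0071, 0.0143, 0.0214 and 0.0286. If Aim 1 gives p = 0.02 and every other p-value exceeds 0.05, Aim 1 ranks first, is compared with 0.0071, and is not significant. It becomes significant only if enough other tests succeed, for example two others at or below 0.0214.

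**Dependence on q.** The plan does not state q. At q = 0.10 (also an assumption), m = 7 and N = 250, Aim 1 power is 65% with the others null and 86% with all real. The Aim 1 threshold could then reach 0.10, which is looser than the 0.05 used for power.

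**The case against.** The strongest reply is that the plan never says Aim 1 is pooled. The adjustment could be meant only for the several secondary outcomes, in keeping with the primary and secondary ranking. That reading is possible, and it is close to the fix below, but nothing in the text states it. The unrestricted wording, and the grouping of all three aims as primary analyses, point the other way.

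A second reply is that the loss may be small. The plan assumes at least 80% power for the other direct effects too. On that assumption Aim 1 keeps about 77% at N = 250, a loss of 3 points. Initiation is taken mainly from data extraction and chart review (Abstract, Methodology; section 5.5), so all 300 may be analysable, and power can then stay above 80%. This stands, and it limits the conclusion.

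Three stronger readings are tempting and are not supported:

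- A reader might infer that the 80% is false. The documents show only that it was not demonstrated under the planned rule. The plan says at least 80%, and some scenarios at N = 300 exceed that.
- A reader might infer that every exploratory, mediation, moderation and add-on test is in the family. The sentence permits this but does not say it. With an assumed 20 tests and the other 19 null, Aim 1 power at N = 250 would be 42%, but no such count appears in the plan.
- A reader might object that FDR control fails to give family-wise protection for the five Aim 3 outcomes. The plan says openly that it controls the one instead of the other. That is a disclosed choice, not an error.

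Nor does pooling inflate the Aim 1 false-positive rate if q is 0.05, since the threshold cannot then exceed 0.05.

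**Conclusion.** The point holds in this form: the decision rule for the primary hypothesis cannot be determined from the plan, and its stated power is not shown under the adjustment the plan adopts. On the natural seven-test reading, Aim 1 power runs from about 55% to 77% at N = 250, and from about 65% to 85% if all 300 are analysable, against 80% and 87% unadjusted. At N = 300 it passes 80% only when most or all of the other effects are real.

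These figures rest on q = 0.05, exactly 80% unadjusted power at N = 250, and independent tests; correlation of 0.3 changes them by about 2 points at most. The missing numeric effect size is a separate gap and prevents any check of the 80% itself.

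**What to change.** Replace the Type 1 Error Protection paragraph with a rule that states the following:

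1. Aim 1, initiation by 6 months, is the single primary test, at two-sided 0.05 and outside any adjustment.
2. Benjamini-Hochberg, at a stated q, applies to six listed secondary tests: Aim 2 sessions and the five Aim 3 outcomes at 6 months.
3. The 1- and 3-month, exploratory, mediation, moderation and add-on tests are reported unadjusted and labelled exploratory. The worst-case logistic regression is a sensitivity analysis of Aim 1 and is not a member of the family.
4. Power for Aims 2 and 3 is restated under that six-test adjustment.

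If the sponsor prefers to keep Aim 1 in the family, the plan should list the tests, give q, and restate Aim 1 power with the assumed effects on the other outcomes.

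The cost is wording, settled before any outcome results by arm are seen, with no added participants or data. The stated power for Aims 2 and 3 will be lower. By the same simulation with m = 6 and q = 0.05, an outcome with exactly 80% unadjusted power has about 77% if the other five are equally strong and about 57% if they are null. The present rule already carries a loss of this kind for those outcomes without stating it.
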